#### 9 EFFICACY ANALYSIS

The efficacy endpoints will be evaluated using RECIST Version 1.1 and presented for the efficacy population.

#### 9.1 Primary Efficacy Analysis

The primary efficacy endpoint of ORR is defined as a best response of CR or PR as determined by the independent radiological review. Response and/or progression are evaluated using the RECIST 1.1 criteria. The ORR will be summarized with frequencies and percentages. The ORR is the best overall response recorded from the start of the treatment until disease progression or the time of the data cutoff. The frequency and percentages of patients with a best overall response of complete response (CR), partial response (PR), stable disease (SD), or progressive disease (PD) will be summarized.

The confirmed response rate will be calculated for patients with sufficient data to determine if the patient has a confirmed response or has progressive disease, otherwise patients will be classified as inevaluable for confirmed response at the time of analysis.

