# 2.2 Sample Size used

Approximately 125 patients are planned to be enrolled under the protocol and subsequent Amendments for the MAA and NDA.

For the initial MAA and NDA submissions all patients enrolled in this trial by the 31st of December 2014 with a data cutoff date of April 2015 will be used for both efficacy and safety conclusions. The efficacy and safety profile for CO-1686 will be established by the combined patients treated in this study and Phase 1 study, CO-1686-008.

Confidential 7 of 17

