#### 4 ANALYSIS POPULATIONS

**Safety Population**—all patients who have received at least one dose of CO-1686.

Efficacy Population—all patients who received at least one dose of CO-1686, have at least one measureable tumor lesion at baseline, and have at least one post-baseline tumor assessment or patients who died before first post-baseline scan. Due to that the efficacy is both assessed by the investigator and the independent radiologist there will be two different efficacy populations:

- Investigator Efficacy-Evaluable Population Flag
- IRR Efficacy-Evaluable Population Flag

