#### 9.2.2 Duration of response

Duration of response (DR) for CR or PR will be calculated as 1+ the number of days from the first response (CR or PR) to documented radiographic progression. Patients without a documented event of radiographic progression will be censored on the date of their last adequate tumor assessment (i.e., radiologic assessment) or date of first response if no subsequent tumor assessments have been performed.

Duration of response will be summarized for both the independent radiology assessment and the investigator assessment.

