#### 9.2.3 Time to first response

The frequency and percentages of patients with a response (CR or PR) will be summarized by the first occurrence using the following time points;  $\leq 9$  weeks (Cycle 2),  $\leq 17$  weeks (Cycle 4),  $\leq 25$  weeks (Cycle 6),  $\leq 33$  weeks (Cycle 8), and  $\geq 33$  weeks.

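### The confirmed response rate in SAP 9.1 and 9.2.1 leaves out patients whose confirmation is unresolved, so at the cutoff it equals or exceeds the rate in the full efficacy population

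*SAP*

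**What the plan says.** SAP 9 sets the general denominator: "The efficacy endpoints will be evaluated using RECIST Version 1.1 and presented for the efficacy population". SAP 4 defines that population so that it takes in dosed patients with measurable disease who "have at least one post-baseline tumor assessment or patients who died before first post-baseline scan". It has one version for the IRR and one for the investigator.

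SAP 9.1 defines the primary endpoint without mentioning confirmation: "The primary efficacy endpoint of ORR is defined as a best response of CR or PR as determined by the independent radiological review". It then adds a further rate: "The confirmed response rate will be calculated for patients with sufficient data to determine if the patient has a confirmed response or has progressive disease", and continues, "otherwise patients will be classified as inevaluable for confirmed response at the time of analysis". SAP 9.2.1 has the same rule for the investigator's assessment. No number of scans, interval or length of follow-up says when data are sufficient. SAP 10.1 says only that missing data are not imputed.

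The analysis set is fixed in SAP 2.2: "For the initial MAA and NDA submissions all patients enrolled in this trial by the 31st of December 2014". SAP 12 puts the data cutoff at 29 April 2015.

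Appendix A of the supplied protocol (Amendment 5) makes best response depend on confirmation, by a scan 4 ± 1 weeks after the first CR or PR. Routine scans are every 8 ± 1 weeks (protocol 9.5.2.1).

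**The concern.** The efficacy population deliberately keeps patients who died before their first scan. The confirmed rate then steps outside that population, by a criterion that depends on outcome and follow-up at the cutoff and is not defined. Responders still awaiting confirmation leave the denominator on any reading. Depending on how the term is read, early deaths, patients with a CR or PR but no later evaluable scan, and patients with ongoing SD may leave too. Two programmers could build different denominators from the same text.

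This SAP governs single-arm analyses for the MAA and NDA, run while patients are still on study. A response rate whose denominator shrinks by an unstated rule is hard to compare with the ORR beside it. The SAP also does not say whether that ORR itself requires confirmation.

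**Working it through.** **1. The plan's own figure.** Protocol Table 11-1 gives 40 [31, 49] for 125 patients. The exact (Clopper-Pearson) 95% interval for 50/125 = 40.0% is 31.3 to 49.1, which agrees. The other rows also reproduce: 38/125 gives 22.5 to 39.3, and 62/125 gives 40.5 to 58.7. The protocol's precision statement therefore rests on all 125 patients.

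**2. Direction at the cutoff.** Let N be the efficacy population, c the confirmed responders at cutoff and d the patients classed as inevaluable. None of the d patients is among the c. The SAP reports c/(N − d), which is at least c/N and equals it only if d = 0 or c = 0.

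**3. Size, as illustration.** The documents give neither c nor d. N = 125 is the planned size; c = 50 and the values of d are assumed.

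| Removed (d) | Rate | Exact 95% CI |
|---|---|---|
| 0 | 50/125 = 40.0% | 31.3 to 49.1 |
| 6 | 50/119 = 42.0% | 33.0 to 51.4 |
| 12 | 50/113 = 44.2% | 34.9 to 53.9 |

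The submission set may be smaller than 125. With N = 100 and c = 40, the rate is 40/95 = 42.1% for d = 5 and 40/90 = 44.4% for d = 10.

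**4. Who is pending.** This step uses the 4 ± 1 week rule of the supplied Appendix A and assumes first dose no later than 31 December 2014.
- From 31 December 2014 to 29 April 2015 is 119 days, or 17.0 weeks.
- 29 April minus 3 weeks is 8 April, so a response first seen after 8 April cannot be confirmed by cutoff.
- 29 April minus 5 weeks is 25 March. A response first seen between 25 March and 8 April may or may not be confirmed, depending on where in its window the second scan falls.
- Last patient, week 8: nominally 25 February, at latest 4 March. Confirmation at latest 5 weeks later is 8 April, before the cutoff.
- Last patient, week 16: nominally 22 April, window 15 to 29 April. A first response there cannot be confirmed in time.

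First responses at week 8 are therefore confirmable on schedule for everyone in the set. Pending cases are mainly later first responses that fall after about 8 April, in early or late enrollees. SAP 9.2.3 has table rows for such later responses, but they are categories and not a forecast.

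**5. Against the eventual rate.** Let k of the d removed patients confirm later, and ignore later confirmations among patients who were kept. Then c/(N − d) exceeds (c + k)/N exactly when k/d < c/(N − d). With assumed N = 125, c = 42 and d = 12, the SAP rate is 42/113 = 37.2% and c/N is 33.6%. The eventual rate is 45/125 = 36.0% if k = 3 and 50/125 = 40.0% if k = 8. Break-even is 12 × 42/113 = 4.46. The SAP rate can fall on either side.

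**6. Whether the primary ORR is confirmed.** Two features of the SAP suggest that it is not. A confirmed rate is given separately, and SAP 9.2.2 censors duration at the "date of first response if no subsequent tumor assessments have been performed", which allows for a responder with no second scan. The supplied Appendix A points the other way. The SAP does not settle it.

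**The case against.** **The primary endpoint stays on the efficacy population.** This stands if the ORR is unconfirmed, as the SAP suggests. A reader might infer that the rule inflates the primary ORR; the documents support that only if the ORR is meant to be confirmed.

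**The number removed could usually be worked out.** SAP 3 presents categorical data as frequencies and percentages, and SAP 5 reports the size of each population. With c, the percentage and N, a reader could normally recover d. This weakens any claim that the exclusions would be hidden. It does not define the term, and it gives no reasons for exclusion.

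**Ongoing SD need not be dropped.** A reader might infer that the denominator is only confirmed responders plus patients with PD. But determining if a patient has one of these outcomes can mean determining whether, and a patient with adequate scans and SD can then be settled as having no confirmed response. Both readings are open, so no magnitude should be built on the exclusion of SD.

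**Pending cases are limited.** This stands for first responses at week 8, as step 4 shows. The assumed values of d have no documentary basis.

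**Counting pending responders as failures is itself a choice.** It is conservative and may understate the eventual rate. That is a reason to show them separately, not to take them out of the denominator.

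**Appendix A comes from Amendment 5, while SAP 1 cites the protocol only through Amendment 3.** This stands. A reader might infer that the SAP departed from the protocol; without the Amendment 3 appendix that cannot be shown. The same caveat applies to the dates in step 4.

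**Conclusion.** The concern holds for the confirmed response rate, by both IRR and investigator. Its denominator departs from the efficacy population through an undefined criterion, and the result at the cutoff equals or exceeds the full-population rate. That direction is arithmetic and needs no assumption. The size does: about 2 points if 6 of 125 patients are removed and about 4 points if 12 are, with 50 confirmed responders assumed. The actual number is not documented.

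The documents do not support the further inference that the reported rate overstates the eventual confirmed rate; step 5 shows it can go either way. The missing label on the primary ORR is a secondary wording point. It matters here because it decides whether the denominator rule reaches the primary result.

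**What to change.** In SAP 9.1 and 9.2.1:

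1. Calculate the confirmed rate over the full IRR (or investigator) efficacy population of SAP 4, counting every patient without a confirmed CR or PR at cutoff as a non-responder.
2. Show responses pending confirmation at cutoff on a separate line, without removing them from the denominator.
3. If the restricted rate is kept, present it as supplementary and show the number excluded.

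As a secondary wording change, label the primary ORR as confirmed or unconfirmed and reconcile it with Appendix A.

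The cost is SAP wording and one table line, with no new patients or scans. The confirmed rate at cutoff becomes equal or lower and may understate the eventual rate; the line of pending responses makes that visible.

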#### 9.2 Secondary Efficacy Analyses

#### 9.2.1 ORR by Investigator Assessment

The ORR is the best overall response recorded from the start of the treatment until disease progression or recurrence as assessed by the investigator.

The frequency and percentages of patients with a best overall response of complete response (CR), partial response (PR), stable disease (SD), or progressive disease (PD) will be summarized.

The confirmed response rate will be calculated for patients with sufficient data to determine if the patient has a confirmed response or has progressive disease, otherwise patients will be classified as inevaluable for confirmed response at the time of analysis.

#### 9.2.2 Duration of response

Duration of response (DR) for CR or PR will be calculated as 1+ the number of days from the first response (CR or PR) to documented radiographic progression. Patients without a documented event of radiographic progression will be censored on the date of their last adequate tumor assessment (i.e., radiologic assessment) or date of first response if no subsequent tumor assessments have been performed.

Duration of response will be summarized for both the independent radiology assessment and the investigator assessment.

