11.2 Statistical Methods

11.2.1 General Considerations

Data will be summarized by T790M status and by dose, but may also be pooled as appropriate.

Quantitative variables will be summarized using descriptive statistics (N, mean, standard deviation, median, minimum, and maximum) and/or frequency and percentages for medically relevant categories. Categorical variables will be presented using frequencies and percentages.

Kaplan-Meier methodology will be used to summarize PFS and OS.

All data will be used to their maximum possible extent but without any imputations for missing data.

All statistical analyses will be conducted with the statistical analysis software (SAS®) System.

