11.2.4.2 Secondary Efficacy Endpoints

BEST OVERALL RESPONSE

The frequency and percentages of best overall responses of CR, PR, SD, or PD will be summarized separately for T790M-positive and T790M-negative patients, and by dose.

DURATION OF RESPONSE

DR for CR and PR will be measured from the date that any of these best responses is first recorded until the first date that PD is objectively documented. DR will be summarized separately for T790M-positive and T790M-negative patients, and by dose, using descriptive statistics (N, mean, standard deviation, median, minimum, and maximum) as well as categorically. For patients who continue treatment post-progression, the first date of progression will be used for the analysis.

DISEASE CONTROL RATE

DCR is defined as the percentage of patients who have achieved CR, PR, and SD lasting at least 12 weeks.

PROGRESSION-FREE SURVIVAL

PFS will be calculated as 1+ the number of days from the first dose of study drug to documented radiographic progression or death due to any cause, whichever occurs first. Patients without a documented event of radiographic progression will be censored on the date of their last adequate tumor assessment (i.e., radiologic assessment) or date of first dose of study drug if no tumor assessments have been performed.

For patients who continue treatment post-progression, the first date of progression will be used for the analysis of PFS.

OVERALL SURVIVAL

OS will be calculated as 1+ the number of days from the first dose of study drug to death due to any cause. Patients without a documented date of death will be censored on the date the patient was last known to be alive.

POPULATION PK ANALYSES

Sparse blood sampling for POPPK analyses will be conducted in all patients treated with CO-1686. A specific POPPK data analysis plan will be developed and will outline the detailed approach to data handling, model development and diagnostics, individual model parameter estimation, exploration of covariate effects, and final model evaluation techniques.

QUALITY OF LIFE

QoL will be measured using the EORTC QLQ-C30, EORTC QLQ-LC13, and the DLQI.^{12,13}

The EORTC questionnaires will be scored using the published scoring algorithms provided by the EORTC. For each item or scale, a linear transformation will be applied to standardize the raw score to a range from 0 to 100. A high scale score represents a higher response level.

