The duration of overall response is measured from the time measurement criteria are met for CR or PR (whichever is first recorded) until the first date that recurrent or PD is objectively documented (taking as reference for PD the smallest measurements recorded since the treatment started).

The duration of overall CR is measured from the time measurement criteria are first met for CR until the first date that recurrent disease is objectively documented.

Duration of Stable Disease

SD is measured from the start of the treatment until the criteria for progression are met, taking as reference the smallest measurements recorded since the treatment started.

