#### 3 GENERAL ANALYSIS CONVENTIONS

Quantitative variables will be summarized using descriptive statistics and may also be summarized categorically with frequencies and percentages. For variables registered on a continuous scale, the following will be presented: N, mean, standard deviation, median, minimum and maximum. Categorical variables will be presented using frequencies and percentages.

The Kaplan-Meier methodology will be used to summarize DR, PFS, and OS. If estimable, the 50th (median) together with a 95% Confidence Interval (CI) will be presented. The number of patients with events and the number of censored patients will also be presented.

All data will be used to their maximum possible extent but without any imputations for missing data.

Unless otherwise specified, baseline is defined as the last measurement on or prior to the first day of study drug administration.

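### Duration of response ignores death: a responder who dies without documented progression is censored as if still responding in the Kaplan-Meier analysis kept for the NDA

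*SAP*

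**What the plan says.** SAP 9.2.2 measures DR "from the first response (CR or PR) to documented radiographic progression". Its censoring rule is general: "Patients without a documented event of radiographic progression will be censored on the date of their last adequate tumor assessment", or on the date of first response if there is no later scan. No exception is made for death. The rule applies to both the independent and the investigator assessment. SAP 3 gives the method: "The Kaplan-Meier methodology will be used to summarize DR, PFS, and OS".

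The protocol uses the same kind of event. Section 11.2.4.2 runs DR "until the first date that PD is objectively documented", and Appendix A runs it "until the first date that recurrent or PD is objectively documented". For PFS, the same protocol section counts time "to documented radiographic progression or death due to any cause, whichever occurs first".

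The summary method differs between the documents. Protocol 11.2.1 says "Kaplan-Meier methodology will be used to summarize PFS and OS" and does not name DR there. Section 11.2.4.2 summarises DR "using descriptive statistics (N, mean, standard deviation, median, minimum, and maximum) as well as categorically".

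SAP 12 lists the analyses left out of the NDA version: PFS by both assessors, OS, disease control rate, quality of life and the exploratory objectives. DR is not on that list.

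**The concern.** A patient who dies can no longer be in response. Censoring at the last scan makes Kaplan-Meier treat that patient as if the later course would have matched that of responders still at risk, which is false for someone who has died. One death can thus end PFS while DR is handled as ongoing, and neither document gives a reason for the difference. The SAP does take account of death elsewhere: its efficacy population (section 4) includes patients who died before the first post-baseline scan.

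With PFS and OS deferred, and time to first response only tabulated by category, no time-to-event efficacy result in the NDA version would reflect a responder's death. A reader would take the DR curve as the durability of benefit, and the error is in the favourable direction.

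A lesser point is that the protocol's mean and standard deviation cannot handle censored durations. The SAP's move to Kaplan-Meier is sound but is not recorded among the changes in SAP 12.

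**Working it through.** The plan states no median, event count or precision for DR, so there is no figure of its own to reproduce.

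**1. Which rule a death falls under**

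| Place | Event that ends the interval | Death |
|---|---|---|
| SAP 9.2.2, DR | documented radiographic progression | not named; general censoring rule applies |
| Protocol 11.2.4.2, DR | documented PD | not named |
| Protocol Appendix A, DR | recurrence or PD | not named |
| Protocol 11.2.4.2, PFS | radiographic progression or death | counted |

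The SAP and protocol agree on the DR event, so this is a shared weakness of definition and not a contradiction between them.

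**2. Are such deaths plausible?** Protocol 3.4.1.1 reports 11 deaths on study or within 28 days of last dose among 148 patients in Study CO-1686-008. Eight were due to progression; the other 3 were pulmonary embolism, pneumonia and unknown cause. Responder status is not given, so no rate for responders follows.

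**3. Effect on the curve.** Let *S* be the true proportion still in response under progression-or-death, and *s* the share of DR events that are deaths without documented progression. The documents do not give *s*; 5%, 10% and 20% are assumed, with no other censoring.

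- Proportional cause-specific hazards: planned curve = S^(1−s). The largest gap is at S = (1−s)^(1/s).
- All such deaths last: at S = 0.50 the planned curve reads 0.50.
- All such deaths first: at S = 0.50 the planned curve reads 0.50/(1−s). The largest gap is *s*, because at S = 1−s the planned curve is still 1.

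| s | Reading at true 50%, proportional | Reading at true 50%, deaths last to deaths first | Gap at true 80%, proportional | Largest gap, proportional | Largest gap, deaths first |
|---|---|---|---|---|---|
| 5% | 0.50^0.95 = 51.8% | 50% to 52.6% | 0.9 points | 1.9 points | 5 points |
| 10% | 0.50^0.90 = 53.6% | 50% to 55.6% | 1.8 points | 3.9 points | 10 points |
| 20% | 0.50^0.80 = 57.4% | 50% to 62.5% | 3.7 points | 8.2 points | 20 points |

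**4. Effect on the median.** With constant hazards the planned median is too long by 1/(1−s), which is 1.053, 1.111 or 1.25. Scans every 8 weeks make the observed median move in steps. A simulation used 40,000 responders, 8-weekly scans, assumed uniform follow-up of 17 to 104 weeks, and deaths censored at the last scan.

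- True median 39 weeks: the proportion in response at 48 weeks was 0.444 against 0.425, 0.468 against 0.427, and 0.506 against 0.423 (SAP rule against death counted, for the three values of *s*). The median moved from 40 to 48, 48 and 56 weeks.
- True median 26 weeks: the median did not move at 5% or 10% (32 weeks under both rules).

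**5. Effect of one death.** Assume all 125 planned patients are in the NDA cut, with the ORRs of Protocol Table 11-1. Responders are 125 × 0.30 = 37.5, 125 × 0.40 = 50 and 125 × 0.50 = 62.5, or about 38, 50 and 63. One such death with all responders at risk lowers the progression-or-death curve by 1/38 = 2.6, 1/50 = 2.0 or 1/63 = 1.6 points. It lowers the planned curve by 0. SAP 2.2 does not give the number in the NDA cut; fewer responders would make each death count for more.

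**6. Follow-up.** From the enrolment limit, 31 December 2014 (SAP 2.2), to the cutoff, 29 April 2015 (SAP 12), is 119 days, or 17.0 weeks. A patient first dosed on the last day has scheduled scans at weeks 8 and 16, plus a confirmatory scan about week 12 if response is seen at week 8 (Appendix A). DR follow-up after a week-8 response is at most 17 − 8 = 9 weeks (8 to 10 with the scan window). This is the shortest case, and earlier patients have more. It shows only that the median may not be estimable, so the curve is the safer scale for judging the effect.

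**The case against.** The strongest reply is that DR has one consistent, prespecified definition in three places. DR and PFS are different endpoints and need not share events, so the curve is too high only against a different estimand. That is correct as far as it goes. But the plan gives no rationale for a progression-only estimand, and censoring a death as uninformative does not describe how long patients stay in response.

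Several mitigating points also stand:

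- Protocol 9.5.2.1 asks for imaging at clinical progression, section 9.4 continues scans after treatment stops, and Appendix A requires a confirmatory scan about 4 weeks after a response. Each gives a chance to document progression before death. However, the first is worded as a recommendation, the second allows exceptions, and none captures a death without progression.
- SAP 2.2 combines this study with CO-1686-008 to establish the efficacy profile. In a pooled DR estimate each death would weigh less.
- Deaths on or soon after treatment appear in the safety tables (SAP 11.1), though not in any efficacy result.
- With 38 to 63 responders and no censoring, the 95% half-width at 50% is about 16 to 12 points (1.96 × √(0.25/n)), wider than every proportional-hazards gap above. Sampling error is not directional, however, and this bias is.
- DR is a secondary, single-arm endpoint with no stated test or threshold, so nothing shows that a conclusion would change.

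These points limit the likely size. They do not remove the bias.

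**Conclusion.** The concern holds. Under SAP 9.2.2 a responder's death without documented progression never counts against DR, and no passage in either document corrects this. Relative to progression-or-death, the expected DR curve is biased upward whenever such deaths occur. In a given sample the median may not move, and the effect is zero if there are none.

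The size cannot be derived from the documents. With proportional hazards and an assumed 5% to 20% share of such deaths, the overstatement at a true 50% is 1.8 to 7.4 points. The deaths-first figures are an extreme bound. The primary ORR is untouched. The change should be made because DR is the only Kaplan-Meier efficacy result in the NDA version and the correction is cheap, but it does not threaten the primary analysis.

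**What to change.** - Define the DR event as documented progression or death from any cause, whichever is first. Censor only patients alive without documented progression, at their last adequate assessment.
- State how a death after two or more missed scheduled scans is handled.
- Use the same definition in SAP 9.2.2, Protocol 11.2.4.2 and Appendix A. Name Kaplan-Meier for DR in the protocol in place of mean and standard deviation.
- Keep the progression-only version as a sensitivity analysis, and report the number of responders who died without documented progression. That count alone shows whether the issue matters.

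**Cost.** For the NDA cut this is wording and programming. Survival status is collected at end of treatment and about every 2 months afterwards (Protocol 5.1.4, 9.3 and 9.4). Since Protocol 3.1 reports the NDA as submitted in mid-2015, it would now be a re-analysis of data already held. Reported DR may be shorter if such deaths occurred.

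One limit should be stated. In the Extension Phase (Appendix C) participation ends after the End of Treatment visit and the schedule has no survival follow-up. Later deaths are therefore not collected, and a final progression-or-death DR for those patients would be incomplete. The NDA cut is not affected.
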